7.8.2 Laboratory data

Date: 07-08-2024, Version 1.0

The analyses of laboratory data will be descriptive in nature and will be based on BI standards (9.3). The up to Week 16 and overall on-treatment period for laboratory analyses will be provided. Note that data from the central laboratory will be used for all displays described below, unless otherwise specified.

For continuous safety laboratory parameters, normalized values will be derived.

Normalization means transformation to a standard unit and to a standard reference range. The process of normalization, handling of repeat values at the same visit for by-visit displays, as well as standard analyses for safety laboratory data are described in the BI guidance for the Display and Analysis of Laboratory Data. All analyses considering multiple times of the ULN (as described below) will be based on standardized and not normalized values. For continuous

Page 42 of 64

c43421787-01

Proprietary confidential information © 2024 Boehringer Ingelheim International GmbH or one or more of its affiliated companies.

safety laboratory parameters, differences to baseline will be calculated. For all outputs, the last assessment before the first treatment at Day 1 is chosen as the baseline value.

Only patients with at least one available post-baseline value will be included in the analysis of an individual laboratory parameter. All individual laboratory data will be listed. Values outside the reference range will be flagged.

For derivation of the last value, the minimum value, and the maximum value, all values during the on-treatment period will be considered. These will be derived for analysis of laboratory, vital signs and local tolerability data. For identification of potentially clinically significant abnormal laboratory values, all values during on-treatment period will also be considered.

Descriptive statistics of laboratory values over time and for the difference from baseline ontreatment will be based upon normalized values, including summaries of the last value on treatment, the minimum value on treatment and the maximum value on treatment and corresponding change from baseline. Graphical displays via box plots/line plots will be produced for the last value, minimum and maximum value on treatment for each continuous laboratory endpoint.

Laboratory values will be compared to their reference ranges; shift tables will be provided for the number of patients with a specific CTCAE grade at baseline versus the CTCAE grade at the last measurement on treatment, as well as the worst grade on treatment; laboratory parameters with exception to this display type are described in the company standards (9.10). These analyses will be based on converted laboratory values. The display of laboratory data using the CTCAE grades will be done based on BI standards (9.10).

Potentially clinically significant abnormalities will be identified based on BI standard rules which are based on converted lab values, i.e. using SI units. These rules will be listed in the SDL appendix of the CTR. Frequency tables will summarize the number of patients with potentially clinically significant abnormalities. Patients having an abnormal lab value at baseline will be presented separately. A separate listing will present potentially clinically significant abnormal lab values; for each functional lab group all patient's lab values will be listed, if there exists at least one lab value with clinically significant abnormality within the group.

The frequency of patients with AST or ALT elevations $\geq 3xULN$, $\geq 5xULN$, $\geq 10xULN$, and $\geq 20xULN$ will be displayed based on standardized laboratory values. To support analyses of liver related adverse drug effects, the frequency of subjects with AST and/or ALT $\geq 3xULN$ combined with the elevation of total bilirubin $\geq 2xULN$, from samples drawn within 30 days of each other, will be displayed, stratified by alkaline phosphatase < 2xULN and $\geq 2xULN$ (a subject can potentially be in both alkaline phosphatase strata in case of multiple AST/ALT and bilirubin elevations). The start of the 30-day time span is triggered by each liver enzyme elevation above the defined thresholds. This analysis will be based on standardized laboratory values.

Date: 07-08-2024, Version 1.0

Proprietary confidential information © 2024 Boehringer Ingelheim International GmbH or one or more of its affiliated companies.

A graphical analysis of ALT and total bilirubin will be performed: the so-called eDISH plot. The peak total bilirubin is presented as a fold increase over the ULN against the peak ALT as a fold increase over the ULN, on a log10 scale. The measurements displayed for total bilirubin and ALT may, or may not, occur on the same date. Two reference lines, 2xULN for total bilirubin and 3xULN for ALT, are drawn onto the graph to divide the plane into four quadrants. Normal cases are in the lower left quadrant, potential DILI cases are in the upper right quadrant (potential Hy's Law quadrant), while the lower right quadrant is known as the Temple's corollary range (ALT $\geq 3xULN$ and total bilirubin < 2xULN). The display will be repeated for AST and total bilirubin.

The frequency of subjects with AST and/or ALT \geq 3xULN combined with the elevation of INR \geq 1.5xULN, from samples drawn within 30 days of each other, will be displayed. The start of the 30-day time span is triggered by each liver enzyme elevation above the defined thresholds. This analysis will be based on standardized laboratory values.

A graphical analysis of ALT and INR will be performed. The peak INR is presented as a fold increase over the ULN against the peak ALT as a fold increase over the ULN, on a log10 scale. The measurements displayed for INR and ALT may, or may not, occur on the same date. Two reference lines, 1.5xULN for INR and 3xULN for ALT, are drawn onto the graph to divide the plane into four quadrants for better visual representation; normal cases are in the lower left quadrant. The display will be repeated for AST and INR.

An additional display will be produced for the frequency of patients with an elevation of the ALT and/or AST \geq 3-fold ULN, and with the appearance of one or more of the following TEAE:

• Fatigue, nausea, vomiting, right upper quadrant pain or tenderness, fever, rash, and/or eosinophilia (>5%).

An occurrence is flagged if, within \pm 7 days of the onset of an AST and/or ALT elevation \geq 3-fold ULN (including events which start or are ongoing through this interval [i.e., including also assessment on the AE stop in addition to the start date]), at least one of the following TEAE terms (excluding PT terms on the secondary path) is observed:

- ADAE.AEHLT = "Gastrointestinal and abdominal pains (excl oral and throat)";
- ADAE.AEDECOD in ("Vomiting", "Fatigue", "Nausea", "Pyrexia", "Right upper quadrant pain", "Abdominal pain upper", "Upper abdominal tenderness");
- ADAE.CQ16NAM = "Skin Rash (BIcMQ narrow);

Date: 07-08-2024, Version 1.0

An occurrence is also flagged if a >5% proportion in the ratio of eosinophils to total white blood cells is observed in the same sample as the detected AST/ALT elevation.

Proprietary confidential information © 2024 Boehringer Ingelheim International GmbH or one or more of its affiliated companies.

Clinically relevant findings in laboratory data will be reported as baseline conditions (at screening) or as AEs (during the trial) if judged clinically relevant by the investigator, and will be analyzed as such.

7.8.3 Vital signs

Descriptive statistics and graphical display are planned for this section of the report.

The analyses of vital signs (blood pressure, pulse rate, body temperature, respiratory rate) will be descriptive in nature. Descriptive statistics of vital signs over time and for the difference from baseline (see Section 6.7) will be provided, including the last value, the minimum value and the maximum value during on-treatment period.

Clinically relevant findings in vital signs data will be reported as baseline conditions (at screening) or as AEs (during the trial) if judged clinically relevant by the investigator, and will be analyzed as such.

7.8.4 ECG

Abnormal findings in 12-lead ECG will be reported as baseline conditions (at screening) or as AEs (during the trial) if judged clinically relevant by the investigator, and will be analyzed as such.

7.8.5 Local Tolerability

Local tolerability will be summarized during on-treatment period and by visit, with the frequency and percentage of patients who experienced any symptoms by severity/intensity.

7.8.6 Acne Episodes

Date: 07-08-2024, Version 1.0

In the final analysis, the occurrence and characteristics of historical acne episodes will be summarised by treatment with frequency and percentage of patients. The characteristics of any acne episodes which occur during the treatment period will be displayed overall; separate displays of the characteristics of those acne episodes which had a) a suspected medical history risk factor, b) a suspected concomitant medication risk factor, and c) a relatedness to spesolimab, will also be presented. If only few records for the acne episodes, listings will be provided instead of summary tables.

Proprietary confidential information © 2024 Boehringer Ingelheim International GmbH or one or more of its affiliated companies.

7.9 OTHER ANALYSIS

7.9.1 Biomarker analyses

The following biomarkers will be analysed and reported as a part of the CTR:

•

For the analysis of values below the lower limit of quantification (LLOQ) or above the upper limit of quantification (ULOQ) will be handled as follows:

Values < LLOQ and values > ULOQ that are reported as numerical values, will be kept as such. Entries reported as text (i.e. "< LLOQ" or "> ULOQ") and for which no value is provided, will be replaced by:

For < LLOQ: 0.5*LLOQFor > ULOQ: ULOQ.

Results on other biomarkers (e.g.

of the

data. In case they are reported outside the CTR the analysis will be defined in a separate document (otherwise the analysis will be described in the CTR).

For the analysis of biomarkers, log transformed data will be used where deemed necessary.

7.9.2 PK/PD analyses

Date: 07-08-2024, Version 1.0

No PK parameters will be calculated.

The descriptive analysis of Spesolimab plasma concentrations will be based on the SAF.

Exclusion of PK concentrations

The ADS ADPC (PK concentrations per time-point or per time-interval) contains column variables ACEXC or ACEXCO indicating inclusion/exclusion (ACEXC) of a concentration and an analysis flag comment (ACEXCO). Exclusion of a concentration depends on the analysis flag comment ACEXCO. For example, if ACEXCO is set to 'ALL CALC', the value will be excluded for all types of analyses based on concentrations. If ACEXCO is set to 'DESC STATS' the value will be excluded from descriptive evaluations per planned time point/time interval. If ACEXCO contains the addition 'TIME VIOLATION' or 'TIME DEVIATION' the value can be used for further analyses based on actual times.

Further details are given in (9.7). No formal analysis of pharmacokinetic/pharmacodynamic relationships is planned.

Proprietary confidential information © 2024 Boehringer Ingelheim International GmbH or one or more of its affiliated companies.

Any further exploratory analyses, if done, will be described in the CTR or in a separate report.

7.9.3 Immunogenicity

Date: 07-08-2024, Version 1.0

The ADA status and titer as well as frequency of patients with ADA to Spesolimab will be presented by visit. Descriptive statistics of ADA titer (for ADA positive patients, when available) will be provided by visit. The number of subjects with ADA status positive/negative at any time will also be presented. ADA parameters (e.g. treatment-induced ADA positive subjects, transient ADA response and persistent ADA response) will also be presented by visit and cumulatively for the overall study duration. Further exploratory assessments of the ADA data will be performed once data is available and these will be described, if done, in the CTR.

Further analyses based on ADA data may be performed such as

- efficacy-based subgroup analysis for selected subgroups in Table 6.5: 1 for the following groups
 - ADA positive and ADA negative subjects (at Week 8 and Week 16 visit), or
 - NAb positive and NAb negative subjects (at Week 8 and Week 16 visit)
- Safety-based subgroup analysis (using e.g. hypersensitivity safety events) for the following groups
 - ADA positive and ADA negative subjects (at any time), or
 - NAb positive and NAb negative subjects (at any time), or

before ADA development (including subjects with events either before their first ADA positive sample or without ADA positive sample throughout) and after ADA development (including subjects with events from the time point of their first ADA positive sample onwards). This approach takes into account the time when ADA actually developed and when the safety event occurred in relationship to ADA.

c43421787-01

Proprietary confidential information © 2024 Boehringer Ingelheim International GmbH or one or more of its affiliated companies.

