## **Immunogenicity**

In healthy volunteers, ADA to spesolimab was developed with a median onset time ranging 4-17 weeks across trials. Overall, the ADA incidence was comparable between i.v. and s.c. administration. The ADA incidence appeared to be higher in females, though the maximum titer was comparable between males and females. Following single dose administrations of s.c. or i.v. spesolimab, the ADA incidence rate was 39%-52% in females, compared with 19~24% in males. The impact of ADA on spesolimab PK was overall mild in healthy volunteers. Following i.v. administration, lowered spesolimab concentration was only observed in 1 subject in trial 1368-0001, and possibly in 2-3 subjects in trial 1368-0043 (all with maximum titer greater than 11 400). Following s.c. administration, ADA formation may have contributed to the lowered spesolimab concentrations in some volunteers with maximum titer higher than 11 400 in trial 1368-0029.

Details of immunogenicity results in other indications can be found in the current Investigator's Brochure (IB) [c03320877-11].

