7.8.1 Adverse Events

Date: 07-08-2024, Version 1.0

Unless otherwise specified, the analyses of AEs will be descriptive in nature, which will include all on-treatment events up to week 8, week 16 treatment, as well as all events during the whole on-treatment period respectively. All analyses of AEs will be based on the number of subjects with AEs and NOT on the number of AEs.

AEs will be coded with the most recent version of MedDRA®. Patients will be analyzed according to the actual treatment received.

The analysis of AEs will be based on the concept of treatment emergent adverse events (TEAE). That means that all AEs occurring between first drug intake till 112 days after last drug intake will be assigned to the on-treatment period. All AEs occurring before first drug intake will be assigned to 'screening' and all AEs occurring after last drug intake + 112 days will be assigned to 'follow-up' (for listings only). For details on the treatment definition, see Table 6.1:1.

The exposure adjusted incidence rate (per 100 patient years) of a selected treatment emergent adverse event is defined as the number of patients experiencing the adverse event per

Proprietary confidential information © 2024 Boehringer Ingelheim International GmbH or one or more of its affiliated companies.

treatment group during time at risk divided by the total time of patients at risk in that treatment group to contribute the event to the analysis multiplied by 100 (per 100 patient years).

Time at risk [patient years] = (date of onset of AE– first treatment start date within that treatment period + 1) / 365.25

If, for a patient, the selected treatment emergent adverse event didn't occur during the above defined treatment period (per Table 6.1:1) then the time at risk will be censored at the earliest of date of death, last contact date per EoS page, or the end of the above defined treatment period.

For each selected treatment emergent AE, the exposure adjusted incidence rate will be calculated as:

Incidence rate [1/100 Patient years (pt-yrs)] = 100 * number of patients with TEAE / Total TEAE-specific time at risk [patient years].

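### The before/after-ADA safety split in SAP 7.9.3 has no time at risk, so it mainly measures person-time; any ADA comparison needs time-varying status

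*SAP*

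**What the plan says.** SAP 7.9.3 introduces this work with "Further analyses based on ADA data may be performed such as", so it is optional. For safety, with hypersensitivity as the example, it lists alternatives.

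- Grouping by status: "ADA positive and ADA negative subjects (at any time), or" the same for neutralising antibodies (NAb).
- Splitting in time. One group is "before ADA development (including subjects with events either before their first ADA positive sample or without ADA positive sample throughout"; the other is "after ADA development (including subjects with events from the time point of their first ADA positive sample onwards". The stated reason is "This approach takes into account the time when ADA actually developed and when the safety event occurred in relationship to ADA".

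The section names no denominator, person-time or time-dependent model. SAP 7.8.1 states "All analyses of AEs will be based on the number of subjects with AEs and NOT on the number of AEs". It also plans an exposure-adjusted rate per 100 patient-years by treatment group, with time at risk counted from the first dose of the treatment period. SAP 7.9.3 does not refer to that rate. The ADA Analysis Set (SAP 6.4) needs a baseline and one reportable post-baseline result. For healthy volunteers, the Immunogenicity part of Protocol 1.2 says "ADA to spesolimab was developed with a median onset time ranging 4-17 weeks across trials", with incidence after single doses of 39–52% in females and 19–24% in males.

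**The concern.** ADA takes weeks to appear, so early follow-up falls almost entirely on the ADA-negative side.

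The time split puts each event on the correct side of the first positive sample, but the two sides cover very different amounts of follow-up. Their event counts would differ even if ADA did nothing.

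Grouping by status at any time classifies people by a later result. If an event shortens follow-up, a participant may never get the chance to test positive and is left in the ADA-negative group.

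Systemic hypersensitivity is an adverse event of special interest (Protocol 5.2.6.1.4, SAP 7.8.1). A table that looks reassuring or alarming for reasons of person-time alone could mislead the longer-term safety reading.

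**Working it through.** The plan gives no figure for this analysis, so there is none to reproduce.

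**Inputs from the documents.** ADA incidence 19–52% and median onset 4–17 weeks, both from healthy volunteers (Protocol 1.2). **Assumed.** Follow-up of 16 or 52 weeks; a mid case of 35% converting at week 10.

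**Step 1: event counts before and after.** Let p be the fraction converting, o the week of first positive, T the follow-up and HR the true hazard ratio after ADA. With a constant baseline hazard and a fixed onset:

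- share of person-time after first positive: a = p(T − o)/T
- expected after/before event ratio: HR × a/(1 − a)
- HR needed for equal counts: (1 − a)/a

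| T (weeks) | p | o (week) | a | Ratio, HR 1 | Ratio, HR 2 | HR for equal counts |
|---|---|---|---|---|---|---|
| 16 | 0.24 | 4 | 0.180 | 0.22 | 0.44 | 4.56 |
| 16 | 0.35 | 10 | 0.131 | 0.15 | 0.30 | 6.62 |
| 16 | 0.52 | 4 | 0.390 | 0.64 | 1.28 | 1.56 |
| 52 | 0.19 | 17 | 0.128 | 0.15 | 0.29 | 6.82 |
| 52 | 0.24 | 4 | 0.222 | 0.28 | 0.57 | 3.51 |
| 52 | 0.52 | 17 | 0.350 | 0.54 | 1.08 | 1.86 |
| 52 | 0.52 | 4 | 0.480 | 0.92 | 1.85 | 1.08 |

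Example, second row: a = 0.35 × 6/16 = 0.131, and 0.131/0.869 = 0.15. With onset at week 17 and 16 weeks of follow-up, *after* is empty.

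**Step 2: dividing by subjects instead.** Take *after* over converters and *before* over everyone. For rare events with no ADA effect the ratio is (1 − o/T)/(1 − a):

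- 19% at week 17 of 52: 0.673/0.872 = 0.77
- 35% at week 10 of 16: 0.375/0.869 = 0.43
- 52% at week 4 of 52: 0.923/0.520 = 1.78

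The bias can go either way. Simulation with log-normal onset, sampling every 4 weeks and 10% baseline event risk gave 0.14–1.59; detection delay shortens the *after* period.

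**Step 3: status at any time.** Risk ratios, positive to negative, from the same simulation:

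| Follow-up | True HR 1 | True HR 2 |
|---|---|---|
| Complete and equal | 0.97–1.02 | 1.31–1.81 |
| 20% random dropout | 1.01–1.14 | – |
| Half of those with an event leave | 0.59–0.95 | 0.76–1.74 |

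Under the null there is no bias with complete, equal follow-up; a real effect is still diluted.

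**Step 4: does the SAP 7.8.1 rate repair it?** Applying that rate, with time from first dose, to status at any time gave 0.50–0.92 at HR 1 when events shorten follow-up. It does not.

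**Step 5: person-time split at first positive.**

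| Method | HR 1 | HR 2 | HR 3 |
|---|---|---|---|
| Crude rate ratio, flat hazard | 0.94–1.03 | – | – |
| Crude rate ratio, hazard tripled in weeks 0–4 | 0.54–0.83 | – | – |
| Stratified by 4-week bands since first dose | 0.93–1.03 | 1.87–2.04 | 2.60–3.01 |

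The time strata are needed, not only the split.

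**The case against.** The strongest reply has four parts.

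1. **Status.** The analysis may or may not be run, safety analysis is descriptive without hypothesis tests (Protocol 7.2.6), and hypersensitivity is tabulated by treatment anyway (SAP 7.8.1). This stands and sets the priority. A reader might infer that the Part 2 dose decision is exposed. The documents tie that decision to the data available at the primary analysis (Protocol 2.1.1) and nowhere make this split an input to it.

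2. **Sampling at the event.** Protocol 4.2.1 asks for an ADA sample when systemic hypersensitivity occurs. It directs permanent discontinuation for anaphylaxis suspected to be drug-caused, not for every reaction. Participants who stop are still expected at end-of-treatment and end-of-study visits, the latter 112 days after the last dose (Protocol 3.3.4.1 and 6). This stands as a limit: a reader might infer that the any-time grouping is biased whatever happens, but that needs unequal or event-shortened follow-up. The ADA schedule is not visible, so the size cannot be fixed.

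3. **Exposure adjustment exists.** SAP 7.8.1 plans rates per 100 patient-years, so it would be wrong to infer that the SAP ignores time at risk. The gap is specific: those rates run from treatment start and are not divided at conversion.

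4. **Person-time alone is no cure.** Correct. If early risk is high, a crude split can make ADA look protective. Closer observation after the first dose than after later doses (Protocol 4.1.5) makes early risk plausible. This changes the remedy rather than removing the problem.

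**Conclusion.** The point holds for the before/after split without any dropout assumption. It lacks a denominator, and the after/before count ratio under no ADA effect ranges from 0.15 to 0.92 across the scenarios tabulated, or zero when onset falls beyond follow-up. At a true hazard ratio of 2 it ranges from 0.29 to 1.85, so a real effect can be hidden. At 19–24% incidence over 52 weeks, a hazard ratio of 3.5 to 6.8 is needed just to reach equal counts.

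For status at any time the point is conditional. Bias under the null arises only if follow-up or sampling is unequal or shortened by the event. The one-sample rule for the ADA set and the discontinuation rule make that plausible; the sample requested at the event reduces it.

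These figures rest on volunteer ADA data and on assumed follow-up, event risk and dropout. They show the mechanism and its possible range, not a forecast for this trial. The primary result is unaffected, and this is a low-priority improvement.

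**What to change.** Add to SAP 7.9.3, for any ADA or NAb safety comparison:

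- Treat status as time-varying, on spesolimab-exposed time only. The clock starts at the first spesolimab dose, so for placebo participants it starts at the switch at Visit 14.
- Split time at risk at the first positive sample. Never-positive participants contribute only *before* time.
- Report events, patient-years and rates per 100 patient-years before and from first positive.
- Stratify by time since first spesolimab dose, or fit a Cox model with time-dependent ADA status.
- Keep status at any time as a descriptive count, not a comparison.

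The cost is SAP wording and modest programming on data already collected. First positive is detection rather than true onset, so some misclassification between samples remains, and strata will be sparse for rare events.
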